# Table 14.3.1.4 Treatment-Emergent Adverse Events During the Double-Blind Period Leading to Study Drug Discontinuation by System Organ Class and Preferred Term Safety Analysis Set

This table will be similar to 14.3.1.2.

Programming note: Replace the first row with "Total number of TEAEs leading to study drug discontinuation" and the second row with "Subjects with any TEAE Leading to Study Drug Discontinuation".

Author:

[name]

Version Number:

Version Date:

Draft 2 09Jan2017 Page **78** of **144** 

Noven Pharmaceuticals, Inc. Protocol HP-3070-GL-04 Page 1 of x

#### Table 14.3.1.5 Treatment-Emergent Adverse Events During the Double-Blind Period Leading to Study Drug Discontinuation by Region and by System Organ Class and Preferred Term Safety Analysis Set

	ND 2020 10 0	ND 2070 0 0 0	
Queter Ormer Class	HP-30/0 18.0 mg	HP-3070 9.0 mg	Placebo
System Organ Class	(N=XXX)	(IN=XXX)	(N=XXX)
Preferred Term	n (%)	n (%)	n (%)
Rest of the World			
Total number of TEAEs Leading	XX	XX	XX
to Study Drug Discontinuation			
Subjects with any TEAE Leading	xx (xx.x)	xx (xx.x)	xx (xx.x)
to Study Drug Discontinuation			
SYSTEM ORGAN CLASS 1	xx (xx.x)	xx (xx.x)	xx (xx.x)
Preferred Term 1	xx (xx.x)	xx (xx.x)	xx (xx.x)
Preferred Term 2	xx (xx.x)	xx (xx.x)	xx (xx.x)
	xx (xx.x)	xx (xx.x)	xx (xx.x)
SYSTEM ORGAN CLASS 2	xx (xx.x)	xx (xx.x)	xx (xx.x)
Preferred Term 1	xx (xx.x)	xx (xx.x)	xx (xx.x)
Preferred Term 2	xx (xx.x)	xx (xx.x)	xx (xx.x)
	xx (xx.x)	xx (xx.x)	xx (xx.x)

Note: TEAE = Treatment-Emergent Adverse Event, AE = Adverse Event, N = number of subjects in the safety analysis set by treatment group.

Note: TEAEs are defined as all AEs which start (or increase in severity) prior to, on or after the date of first dose of doubleblind study medication through the 30 day follow-up period.

Note: Percentages are calculated as (n/N)\*100.

Note: Subjects with multiple events in the same category are counted only once in that category. Subjects with events in more than one category are counted once in each of those categories.

Note: This summary is sorted by decreasing frequency of system organ class, and within system organ class, by decreasing frequency of preferred term in the HP-3070 18.0mg column.

Note: Adverse events are coded using Medical Dictionary for Regulatory Activities (MedDRA) Version xx.x.

Noven\HP-3070\XWA17541\Biostatistics\Production\Tables\xxxxx.sas ddmmmyyyy hh:mm

Programming note: SOC should be displayed in all caps. Preferred Term should include lower case. Repeat table for each region: Rest of

 Author:
 [name]
 Version Number:
 Draft 2

 Version Date:
 09Jan2017

 Page 79 of 144

the World, Russia then North America.

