### Denominators:

- If a different count other than the population count is used for a denominator (within the table) to calculate percentages, there should be a row in the table that identifies that number "N".
- Alternatively, a footnote should be included in each table with percentages to indicate the denominator for percentages.

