### Table 14.1.3 Disposition During the Double-Blind Period All Analysis Sets

	HP-3070 18.0 mg (N=xxx) n (%)	HP-3070 9.0 mg (N=xxx) n (%)	Placebo (N=xxx) n (%)	Overall (N=xxx) n (%)
PK Analysis Set				
Number of Subjects who Completed the Study	xx (xx.x)	xx (xx.x)	xx (xx.x)	xx (xx.x)
Number of Subjects who Discontinued the Study	xx (xx.x)	xx (xx.x)	xx (xx.x)	xx (xx.x)
Primary reason for early discontinuation				
Adverse event	xx (xx.x)	xx (xx.x)	xx (xx.x)	xx (xx.x)
Death	xx (xx.x)	xx (xx.x)	xx (xx.x)	xx (xx.x)
Non-compliance	xx (xx.x)	xx (xx.x)	xx (xx.x)	xx (xx.x)
Lack of efficacy	xx (xx.x)	xx (xx.x)	xx (xx.x)	xx (xx.x)
Subject requires treatment with a prohibited medication	xx (xx.x)	xx (xx.x)	xx (xx.x)	xx (xx.x)
Pregnancy	xx (xx.x)	xx (xx.x)	xx (xx.x)	xx (xx.x)
Physician decision	xx (xx.x)	xx (xx.x)	xx (xx.x)	xx (xx.x)
Study terminated by investigator	xx (xx.x)	xx (xx.x)	xx (xx.x)	xx (xx.x)
Study terminated by sponsor	xx (xx.x)	xx (xx.x)	xx (xx.x)	xx (xx.x)
Subject withdrew consent	xx (xx.x)	xx (xx.x)	xx (xx.x)	XX (XX.X)
Other	xx (xx.x)	xx (xx.x)	xx (xx.x)	xx (xx.x)

Note: ITT = Intent-to-treat, PK = Pharmacokinetic, N = number of subjects in the ITT analysis set by treatment group.

Note: Percentages are calculated as (n/N)\*100.

Note: This summary is based on data recorded in the eCRF.

Noven\HP-3070\XWA17541\Biostatistics\Production\Tables\xxxxx.sas ddmmmyyyy hh:mm

Author:

[name]

Version Number:

Version Date:

Draft 2 09Jan2017 Page **22** of **144**  Noven Pharmaceuticals Version No. 1.0

Noven Pharmaceuticals, Inc. STATISTICAL ANALYSIS PLAN: PROTOCOL HP-3070-GL-04

Noven Pharmaceuticals, Inc. Protocol HP-3070-GL-04

Page 1 of x

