### Table 14.2.3.1.5 Treatment Comparison of Change from Baseline in PANSS Total Score at Weeks 1 – 6 by Completion Status Full Analysis Set

			Treatment Group Comparison			
		Treatment Group			(Active - Placebo)	
	HP-3070 18.0 mg	HP-3070 9.0 mg	Placebo	HP-3070 18.0 mg	HP-3070 9.0 mg	
Statistic	(N=XXX)	(N=xxx)	(N=XXX)	(N=XXX)	(N=XXX)	
Change from Baseline						
to Week 1						
n	XX	XX	XX			
Mean	x.x	х.х	x.x			
SD	x.xx	x.xx	x.xx			
Median	х.х	х.х	х.х			
Min	х	х	х			
Max	х	х	Х			
LSM estimate	х.х	х.х	х.х	x.x	x.x	
SE	x.xxx	x.xxx	x.xxx	x.xxx	x.xxx	
95% CI	x.xx, x.xx	x.xx, x.xx	x.xx, x.xx	x.xx, x.xx	x.xx, x.xx	
p-value				x.xxx	x.xxx	

Note: PANSS = Positive and Negative Syndrome Scale, LSM = Least Squares Mean, SE = Standard Error, CI = Confidence Interval, N = number of subjects in the full analysis set by treatment group and completion status.

Note: The PANSS total score is the sum of all 30 items. Higher values represent greater severity of illness. If one or more items are missing at a given assessment, the total score is set to missing.

Note: Baseline is defined as the last non-missing measurement taken prior to first dose of double-blind study medication.

Note: The mixed linear repeated measures model includes treatment, country, visit, treatment by visit interaction, and baseline value as covariates, and subject as random effect. The correlation of repeated measures within a subject is estimated with an unstructured covariance matrix. The Kenward-Rogers method is used to estimate the denominator degrees of freedom.

Noven\HP-3070\XWA17541\Biostatistics\Production\Tables\xxxxx.sas ddmmmyyyy hh:mm Programming note: Repeat for weeks 2-6, then repeat for subjects who discontinued the study.

Author:

[name]

Version Number: Version Date:

Draft 2

Page 54 of 144

09Jan2017

106

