#### Table 14.3.1.7 Serious Treatment-Emergent Adverse Events During the Double-Blind Period by Region and by System Organ Class and Preferred Term Safety Analysis Set

Safety Analysis Set

This table will be similar to 14.3.1.5. Programming note: Replace the first row with "Total number of serious TEAEs" and the second row with "Subjects with any Serious TEAE".

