### Table 14.3.1.11 Commonly Occurring (>= 5%) Treatment-Emergent Adverse Events During the Double-Blind Period by Region and by System Organ Class and Preferred Term

Safety Analysis Set

This table will be similar to 14.3.1.5. Add a footnote: Note: Commonly Occurring TEAE is defined as any TEAE occurring in at least 5% of subjects in any treatment arm.

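### The by-region adverse event tables count subjects in one region but divide by the whole arm's N, so the printed percentages are not regional incidences

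*SAP*

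**What the plan says.** Table 14.3.1.5 shows n (%) by system organ class and preferred term, with Rest of the World as the worked block. Its programming note says "Repeat table for each region: Rest of" the World, then Russia, then North America. The N footnote reads "N = number of subjects in the safety analysis set by treatment group". The percentage note begins "Percentages are calculated as (n/N" and multiplies by 100. The N placeholder sits in the column header, above the region label. No row gives a regional N.

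Three other tables inherit the shell. Table 14.3.1.7 (serious TEAEs by region) says "This table will be similar to 14.3.1.5", and Tables 14.3.1.11 and 14.3.1.12 (common events by region) say the same. Table 14.3.1.11 adds: "Note: Commonly Occurring TEAE is defined as any TEAE occurring in at least 5% of subjects in any treatment arm". That matches Section 16.1.5, which also sets the 5% threshold by treatment arm.

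The Denominators rule in the output conventions covers this situation: "If a different count other than the population count is used for a denominator (within the table) to calculate percentages", the table needs a row showing that N or, alternatively, a footnote naming the denominator. Some shells do qualify N. The second page of Table 14.2.3.1.5 has "N = number of subjects in the full analysis set by treatment group and completion status", and Table 14.3.2.9 uses the subjects with data at each visit.

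A related note appears in Table 14.1.3 (disposition). The blocks for the Full, Safety and PK Analysis Sets all carry "N = number of subjects in the ITT analysis set by treatment group".

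**The concern.** A subject enrolled in Russia cannot contribute an event to the North America block, so that subject does not belong in the block's denominator when the percentage is read as the North American rate. A by-region adverse event table is read for exactly that rate. With the arm-wide N, two regions with the same underlying incidence print different percentages simply because they enrolled different numbers.

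These four tables are the only shells that break adverse events down by region. What is at stake is whether a reader can judge if discontinuations for adverse events, serious events or common events are more frequent in one region than another, and how large the regional rates are.

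**Working it through.** **Inputs**
- Numerator: affected subjects in one region and arm, n_r (Table 14.3.1.5, repeated by region).
- Denominator as written: N_arm, the arm's safety-set count (footnote of the same table).
- Denominator for a regional incidence: N_r, the safety-set subjects in that region and arm.
- Illustrative arm size: 204 (SAP Section 3.1, planned evaluable subjects per arm).
- Regional shares of the arm, N_r/N_arm: not given in the SAP, so a range of 10% to 60% is assumed.

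The plan states no figure here to reproduce; the check is of the formula.

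**Identity**

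Printed % = 100 × n_r/N_arm = 100 × (n_r/N_r) × (N_r/N_arm) = true regional % × region's share of the arm.

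**Range over assumed shares**

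| Assumed share | True 10% prints as | True 5% prints as |
|---|---|---|
| 10% | 1.0% | 0.5% |
| 20% | 2.0% | 1.0% |
| 30% | 3.0% | 1.5% |
| 40% | 4.0% | 2.0% |
| 50% | 5.0% | 2.5% |
| 60% | 6.0% | 3.0% |

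**Whole-number example** (assumed split of 204 into 102, 61 and 41)

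| N_r | Affected | Regional incidence | Printed with N = 204 |
|---|---|---|---|
| 102 | 10 | 10/102 = 9.8% | 10/204 = 4.9% |
| 61 | 6 | 6/61 = 9.8% | 6/204 = 2.9% |
| 41 | 4 | 4/41 = 9.8% | 4/204 = 2.0% |

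Three equal regional rates print as 4.9%, 2.9% and 2.0%. The printed values add to the arm's rate (20/204 = 9.8%), so they are correct as shares of the arm.

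**Ratio and difference between arms.** Take a region holding 20% of each arm, with a true 10% on active and 5% on placebo. The table prints 2.0% and 1.0%. The ratio stays at 2, but the risk difference shrinks from 5 percentage points to 1.

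**The 5% tables.** If events are selected on the arm-wide rate, the event in the example (9.8% in the arm) qualifies. The table headed as showing events of at least 5% then prints it as 4.9%, 2.9% and 2.0%. With regional denominators it prints as 9.8% in each block.

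**Table 14.1.3.** With the ITT count as N, completed plus discontinued in a block equals 100 × N_set/N_ITT. That is below 100% whenever the set is smaller than ITT. If placebo subjects are not in the PK set, 1:1:1 randomization caps that block's Overall column at 2/3, about 67%.

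**The case against.** The best defence is that the unit being repeated is a whole table with its own N placeholder, so a programmer could enter a regional N in each repeat. The footnote is boilerplate shared with the unstratified Table 14.3.1.2. The shells are not consistent elsewhere either: the first page of Table 14.2.3.1.5 lacks the completion-status qualifier that its second page has. An unqualified footnote is therefore weak evidence of a deliberate arm-wide denominator. This stands as an account of how the wording arose. It does not rescue the wording, because a regional N in the header would make the printed footnote false.

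It is also fair that raw counts are printed and that Tables 14.1.2 and 14.1.5 give regional counts by arm for the ITT set, so a careful reader could approximate the regional rates. Section 16 plans no between-group tests on safety data unless specified.

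Two stronger readings are tempting, and the SAP does not support either:
- **Under-selection of common events.** A reader might infer that a region with a 20% share needs a true rate of 25% before an event is listed as common. That would follow only if the threshold were applied to the printed regional percentages. Section 16.1.5 and the footnote to Table 14.3.1.11 set it by treatment arm.
- **PK disposition percentages too low by a third.** A reader might infer this from an exclusion reason in Table 14.1.1, namely that no active patch was applied. Section 5.5 does not itself exclude placebo, and the PK blocks of Tables 14.1.1 and 14.1.3 keep a Placebo column. The two-thirds cap is therefore conditional. An ITT base also has precedent in Table 14.1.1, and in Table 14.1.3 it is at least disclosed.

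**Conclusion.** The point holds for the four by-region adverse event tables. Followed as written, they print true regional incidence times the region's share of the arm. Under assumed shares of 10% to 60%, a true 10% appears as 1% to 6%; the actual size depends on enrolment that the SAP does not report. Absolute regional rates, risk differences and between-region comparisons are distorted.

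The limits are equally clear. The figures are not false as fractions of the arm. Country-stratified 1:1:1 randomization should keep each region's share similar across arms, so between-arm ratios within a region are largely preserved. The tables are descriptive, and no efficacy or inferential result depends on them.

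The Table 14.1.3 denominator is a secondary matter of presentation. Whether placebo belongs in the PK set is an inconsistency to reconcile, not an established error.

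**What to change.** - **Tables 14.3.1.5, 14.3.1.7, 14.3.1.11 and 14.3.1.12:** extend the N footnote so that it counts safety-set subjects by treatment group and by region, and print that N under each region heading. This also satisfies the Denominators rule in the output conventions.
- **Tables 14.3.1.11 and 14.3.1.12:** keep the 5% selection by treatment arm, as in Section 16.1.5. Add a note that events are selected on the arm-wide rate and then displayed with regional denominators.
- **Table 14.1.3:** use each block's own analysis-set N, so that completed plus discontinued sums to 100% within the block.
- **PK set:** reconcile Section 5.5, the exclusion reason in Table 14.1.1 and the Placebo columns in the PK blocks of Tables 14.1.1 and 14.1.3, so that it is clear whether placebo subjects belong.

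The cost is shell footnote and header edits, plus one clarification of the PK set. No data collection, model or test changes.

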### Table 14.3.1.6 Serious Treatment-Emergent Adverse Events During the Double-Blind Period by System Organ Class and Preferred Term

#### Safety Analysis Set

This table will be similar to 14.3.1.2. Programming note: Replace the first row with "Total number of serious TEAEs" and the second row with "Subjects with any Serious TEAE".

#### Table 14.3.1.7 Serious Treatment-Emergent Adverse Events During the Double-Blind Period by Region and by System Organ Class and Preferred Term Safety Analysis Set

Safety Analysis Set

This table will be similar to 14.3.1.5. Programming note: Replace the first row with "Total number of serious TEAEs" and the second row with "Subjects with any Serious TEAE".

### Table 14.3.1.8 Serious Treatment-Emergent Adverse Events During the Double-Blind Period by System Organ Class, Preferred Term, Relationship to Study Medication, and Severity

#### Safety Analysis Set

This table will be similar to 14.3.1.3. Programming note: Replace the first row with "Subjects with any Serious TEAE".

### Table 14.3.1.9 Treatment-Emergent Adverse Events During the Double-Blind Period Leading to Death by System Organ Class and Preferred Term

#### Safety Analysis Set

This table will be similar to 14.3.1.2. Programming note: Replace the first row with "Total number of TEAEs leading to death" and the second row with "Subjects with any TEAE Leading to Death".

## Table 14.3.1.10 Commonly Occurring (>= 5%) Treatment-Emergent Adverse Events During the Double-Blind Period by System Organ Class and Preferred Term

Safety Analysis Set This table will be similar to 14.3.1.2. Add a footnote:

Note: Commonly Occurring TEAE is defined as any TEAE occurring in at least 5% of subjects in any treatment arm.

Author: [name]

Version Number: Version Date: Draft 2 09Jan2017 Page **80** of **144** 

Protocol No. HP-3070-GL-04 14 September 2018

Noven Pharmaceuticals, Inc. STATISTICAL ANALYSIS PLAN: PROTOCOL HP-3070-GL-04

### Table 14.3.1.11 Commonly Occurring (>= 5%) Treatment-Emergent Adverse Events During the Double-Blind Period by Region and by System Organ Class and Preferred Term

Safety Analysis Set

This table will be similar to 14.3.1.5. Add a footnote: Note: Commonly Occurring TEAE is defined as any TEAE occurring in at least 5% of subjects in any treatment arm.

### Table 14.3.1.12 All Commonly Occurring (>= 5%) Adverse Events During the Double-Blind Period by Region and by System Organ Class and Preferred Term

Safety Analysis Set

This table will be similar to 14.3.1.5. Add a footnote: Note: Commonly Occurring AE is defined as any AE occurring in at least 5% of subjects in any treatment arm.

### Table 14.3.1.13 Commonly Occurring (>= 2%) Treatment-Emergent Adverse Events During the Double-Blind Period by System Organ Class and Preferred Term

#### Safety Analysis Set

This table will be similar to 14.3.1.2. Add a footnote: Note: Commonly Occurring TEAE is defined as any TEAE occurring in at least 2% of subjects in any treatment arm.

Author:

[name]

Version Number: Version Date: Draft 2 09Jan2017 Page **81** of **144** 

Noven Pharmaceuticals, Inc. Protocol HP-3070-GL-04 Page 1 of x

Draft 2

Page 82 of 144

09Jan2017

## Table 14.3.1.14 Treatment-Emergent Adverse Events at Patch Application Site During the Double-Blind Period by Preferred Term and Severity Safety Analysis Set

	HP-3070 18.0 mg	HP-3070 9.0 mg	Placebo
Preferred Term	(N=XXX)	(N=XXX)	(N=xxx)
Severity	n (%)	n (%)	n (%)
Total number of Dermal TEAEs	XX	XX	XX
Subjects with any Dermal TEAE	xx (xx.x)	xx (xx.x)	xx (xx.x)
Preferred Term 1	xx (xx.x)	xx (xx.x)	xx (xx.x)
Mild	xx (xx.x)	xx (xx.x)	xx (xx.x)
Moderate	xx (xx.x)	xx (xx.x)	xx (xx.x)
Severe	xx (xx.x)	xx (xx.x)	xx (xx.x)
Preferred Term 2	xx (xx.x)	xx (xx.x)	xx (xx.x)
Mild	xx (xx.x)	xx (xx.x)	xx (xx.x)
Moderate	xx (xx.x)	xx (xx.x)	xx (xx.x)
Severe	xx (xx.x)	xx (xx.x)	xx (xx.x)
Preferred Term 3	xx (xx.x)	xx (xx.x)	xx (xx.x)
Mild	xx (xx.x)	xx (xx.x)	xx (xx.x)
Moderate	xx (xx.x)	xx (xx.x)	xx (xx.x)
Severe	xx (xx.x)	xx (xx.x)	xx (xx.x)

Note: TEAE = Treatment-Emergent Adverse Event, AE = Adverse Event, N = number of subjects in the safety analysis set by treatment group.

Note: TEAEs are defined as all AEs which start (or increase in severity) prior to, on or after the date of first dose of doubleblind study medication through the 30 day follow-up period.

Note: TEAEs with a missing severity are counted as severe.

Note: Percentages are calculated as (n/N)\*100.

Note: Subjects with multiple events in the same category are counted only once in that category. Subjects with events in more than one category are counted once in each of those categories.

Note: This summary is sorted by decreasing frequency of preferred term in the HP-3070 18.0mg column.

Note: Adverse events are coded using Medical Dictionary for Regulatory Activities (MedDRA) Version xx.x.

Noven\HP-3070\XWA17541\Biostatistics\Production\Tables\xxxxx.sas ddmmmyyyy hh:mm

 Author:
 [name]
 Version Number:

 Version Date:
 Version Date:

134

Noven Pharmaceuticals Version No. 1.0

Protocol No. HP-3070-GL-04 14 September 2018

Noven Pharmaceuticals, Inc. STATISTICAL ANALYSIS PLAN: PROTOCOL HP-3070-GL-04

IMS Health & Quintiles are now

Noven Pharmaceuticals, Inc. Protocol HP-3070-GL-04

Page 1 of x

Laboratory Test (SI Unit)	Visit	Statistic	HP-3070 18.0 mg (N=xxx)	HP-3070 9.0 mg (N=xxx)	Placebo (N=xxx)
Hemoglobin (g/dL)					
	Baseline	n	XX	XX	XX
		Mean	XX.X	xx.x	XX.X
		SD	xx.xx	xx.xx	XX.XX
		Median	XX	XX	xx
		Min	XX	XX	XX
		Max	XX	XX	xx
	Week 3	n	XX	XX	XX
		Mean	XX.X	XX.X	XX.X
		SD	xx.xx	xx.xx	xx.xx
		Median	XX	XX	xx
		Min	XX	XX	XX
		Max	XX	XX	XX
	Change from Baseline to Week 3	n	XX	XX	xx
		Mean	xx.x	XX.X	xx.x
		SD	XX.XX	xx.xx	XX.XX
		Median	XX	xx	XX
		Min	XX	XX	XX
		Max	XX	XX	xx

Table 14.3.2.1 Clinical Laboratory Quantitative Results and Change from Baseline by Visit - Hematology Safety Analysis Set

Note: Baseline is defined as the last non-missing measurement taken prior to first dose of double-blind study medication. Note: Unscheduled visits are not included in this summary.

Noven\HP-3070\XWA17541\Biostatistics\Production\Tables\xxxxx.sas ddmmmyyyy hh:mm

Programming note: Repeat at week 6 and for all tests planned in the protocol

Author:

[name]

Version Number: Version Date:

Draft 2 09Jan2017 Page 83 of 144 Noven Pharmaceuticals Version No. 1.0 Protocol No. HP-3070-GL-04 14 September 2018

Noven Pharmaceuticals, Inc. STATISTICAL ANALYSIS PLAN: PROTOCOL HP-3070-GL-04

Table 14.3.2.2 Clinical Laboratory Quantitative Results and Change from Baseline by Visit – Serum ChemistrySafety Analysis SetThis table will be similar to 14.3.2.1.

Table 14.3.2.3 Clinical Laboratory Quantitative Results and Change from Baseline by Visit – Urinalysis Safety Analysis Set

This table will be similar to 14.3.2.1.

Author: Ama

[name]

Version Number: Version Date: Draft 2 09Jan2017 Page **84** of **144** 

IMS Health & Quintiles are now

Noven Pharmaceuticals, Inc. Protocol HP-3070-GL-04 Page 1 of x

#### Table 14.3.2.4 Clinical Laboratory Shifts from Baseline to Worst On-Treatment Result for Categorical Measurements Safety Analysis Set

				Woi	rst On-Treatm	ent Result		
			Negative	Trace	1+	2+	3+	4+
Laboratory Test	Treatment Group	Baseline Result	n (%)	n (%)	n (%)			
Categorical Lab								
Test 1								
	HP-3070 18.0 mg	Negative	xx (xx.x)	xx (xx.x)	xx (xx.x)	xx (xx.x)	xx (xx.x)	xx (xx.x)
	(N=XX)							
		Trace	xx (xx.x)	xx (xx.x)	xx (xx.x)	xx (xx.x)	xx (xx.x)	xx (xx.x)
			xx (xx.x)	xx (xx.x)	xx (xx.x)	xx (xx.x)	xx (xx.x)	xx (xx.x)
	HP-3070 9.0 mg	Negative	xx (xx.x)	xx (xx.x)	xx (xx.x)	xx (xx.x)	xx (xx.x)	xx (xx.x)
	(N=XX)							
		Trace	xx (xx.x)	xx (xx.x)	xx (xx.x)	xx (xx.x)	xx (xx.x)	xx (xx.x)
			xx (xx.x)	xx (xx.x)	xx (xx.x)	xx (xx.x)	xx (xx.x)	xx (xx.x)
	Placebo (N=XX)	Negative	xx (xx.x)	xx (xx.x)	xx (xx.x)	xx (xx.x)	xx (xx.x)	xx (xx.x)
		Trace	xx (xx.x)	xx (xx.x)	xx (xx.x)	xx (xx.x)	xx (xx.x)	xx (xx.x)
			xx (xx.x)	xx (xx.x)	xx (xx.x)	xx (xx.x)	xx (xx.x)	xx (xx.x)

Note: N is the number of subjects with both baseline and post-baseline assessments in a treatment group.

Note: Worst on-treatment result is defined as the worst result occurring after the administration of the first dose of double-blind study medication.

Note: Baseline is defined as the last non-missing measurement taken prior to first dose of double-blind study medication.

Note: Percentages are calculated as (n/N) \* 100.

 $\label{eq:Noven_HP-3070_XWA17541} Biostatistics \Production_Tables \xxxxx.sas \ ddmmmyyyy \ hh:mm \ Programming \ note: \ Repeat \ for \ all \ tests \ planned \ in \ the \ protocol$ 

Author: Am

[name]

Version Number: Version Date: Draft 2 09Jan2017 Page **85** of **144** 

Noven Pharmaceuticals, Inc. Protocol HP-3070-GL-04 Page 1 of x

Table 14.3.2.5.1 Clinical Laboratory Shifts from Baseline to Maximum On-Treatment Result -	· Hematology
Safety Analysis Set	

			Wc	orst On-Treatment Resu	ılt
			Low	Normal	High
Laboratory Test	Treatment Group	Baseline Result	n (%)	n (%)	n (%)
Hemoglobin					
	HP-3070 18.0 mg (N=XX)	Low	xx (xx.x)	xx (xx.x)	xx (xx.x)
		Normal	xx (xx.x)	xx (xx.x)	xx (xx.x)
		High	xx (xx.x)	xx (xx.x)	xx (xx.x)
	HP-3070 9.0 mg (N=XX)	Low	xx (xx.x)	xx (xx.x)	xx (xx.x)
		Normal	xx (xx.x)	xx (xx.x)	xx (xx.x)
		High	xx (xx.x)	xx (xx.x)	xx (xx.x)
	Placebo (N=XX)	Low	xx (xx.x)	xx (xx.x)	xx (xx.x)
		Normal	xx (xx.x)	xx (xx.x)	xx (xx.x)
		High	xx (xx.x)	xx (xx.x)	xx (xx.x)

Note: N is the number of subjects with both baseline and post-baseline assessments in a treatment group.

Note: Maximim on-treatment result is defined as the maximum result occurring after the administration of the first dose of doubleblind study medication.

Note: Baseline is defined as the last non-missing measurement taken prior to first dose of double-blind study medication.

Note: Percentages are calculated as (n/N) \* 100.

Note: Low is less than the normal low range value, Normal is inclusive of the normal low and high range values, and High is greater than the normal high range value.

Noven\HP-3070\XWA17541\Biostatistics\Production\Tables\xxxxx.sas ddmmmyyyy hh:mm Programming note: Repeat for all tests planned in the protocol

Author:

[name]

Version Number: Version Date: Draft 2 09Jan2017 Page **86** of **144** 

Protocol No. HP-3070-GL-04 14 September 2018

Noven Pharmaceuticals, Inc. STATISTICAL ANALYSIS PLAN: PROTOCOL HP-3070-GL-04

 Table 14.3.2.5.2 Clinical Laboratory Shifts from Baseline to Minimum On-Treatment Result – Hematology

 Safety Analysis Set

This table will be similar to 14.3.2.5.1.

Table 14.3.2.6.1 Clinical Laboratory Shifts from Baseline to Maximum On-Treatment Result – Serum Chemistry Safety Analysis Set This table will be similar to 14.3.2.5.1.

Table 14.3.2.6.2 Clinical Laboratory Shifts from Baseline to Minimum On-Treatment Result – Serum ChemistrySafety Analysis SetThis table will be similar to 14.3.2.5.1.

 Table 14.3.2.7.1 Clinical Laboratory Shifts from Baseline to Maximum On-Treatment Result – Urinalysis

 Safety Analysis Set

 This table will be similar to 14.3.2.5.1.

Table 14.3.2.7.2 Clinical Laboratory Shifts from Baseline to Minimum On-Treatment Result – UrinalysisSafety Analysis SetThis table will be similar to 14.3.2.5.1.

Author:

[name]

Version Number: Version Date:

Draft 2 09Jan2017 Page **87** of **144** 

Noven Pharmaceuticals, Inc. Protocol HP-3070-GL-04 Page 1 of x

